## 2.2.2 Rationale for evaluation of 3M-052-AF alone (addition of Part B)

3M-052-AF adjuvant was evaluated in a cynomolgus macaque study with and without Alum in a study of a coronavirus vaccine candidate. This receptor-binding domain (RBD) sortase A-conjugated ferritin nanoparticle (RBD-scNP) vaccine consists of a 24-mer SARS-CoV-2 RBD nanoparticle conjugated to a ferritin scaffold (19).

**Figure 2-4 Neutralizing antibodies and in vivo protection elicited by RBD-scNP vaccine formulated with three different adjuvants.**

(A) Schematic of the vaccination and challenge study. Cynomolgus macaques (n=5 per group) were immunized intramuscularly 3 times with 100 µg of RBD-scNP adjuvanted with 3M-052-AF, Alum, 3M052-AF, or PBS control. Animals injected with adjuvant alone or PBS were set as control groups. Monkeys were then challenged with SARS-CoV-2 WA-1, collected for blood, Bronchoalveolar lavage (BAL) and nasal swab samples, and necropsied for pathologic analysis. (B) Neutralization titers of plasma antibodies (post-3rd immunization) against pseudovirus of

SARS-CoV-2 variants in 293T-ACE2-TMPRSS2. **(C)** Reduction of ID50 titers against variants shown as fold reduction compared to the titers against WA-1. **(D-E)** Neutralization titers of plasma antibodies (post-3rd immunization) against pseudoviruses of the SARS-CoV-2 Omicron (BA.1 and BA.2) variants, SARS-CoV-2 PMS20 variant, and SARS-CoV in 293T-ACE2 cells. For SARS-CoV-2 variants, the geometric mean titers and the fold reduction compared to D614G are shown. **(F)** SARS-CoV-2 N gene sgRNA in BAL and nasal swab samples collected on day 2 and 4 post-challenge. Dashed line indicates limit of the detection. **(G)** Histopathological analysis. Lung sections from each animal were scored for lung inflammation by haematoxylin and eosin (H&E) staining, and for SARS-CoV-2 nucleocapsid antigen (Ag) expression by immunohistochemistry (IHC) staining. ns, not significant, \* $P < 0.05$ , Wilcoxon rank sum exact test.

The RBD-scNP (100 µg) was administered intramuscularly in the right and left quadriceps at 3 timepoints with or without adjuvant as defined in [Figure 2-4](#), Panel A. Surprisingly we found that 3M-052-AF in each assay out-performed or was not inferior to the other formulations ([Figure 2-4](#)). In the cynomolgus monkey study ([Figure 2-4](#) Panel A), the antibodies induced by 3M-052-AF adjuvant with the RBD-sortase conjugated ferritin nanoparticle (scNP) induced higher neutralizing antibodies for many SARS-CoV-2 variants ([Figure 2-4](#) Panel B). Of great interest is the finding that 3M-052-AF alone induced higher titers to Omicron compared to 3M-052/Alum or Alum alone ([Figure 2-4](#)). After 2 or 3 immunizations, the combination of 3M-052/Alum was the lower value for Omicron neutralization and 3M-052-AF alone was the higher titer. Panels F and G of [Figure 2-4](#) demonstrate the results of challenge of the monkeys after three immunizations and show protection with all adjuvant formulations with the least complete protection in the Alum alone group. All adjuvant combinations were well tolerated in this study. There were no deaths. Animals were monitored for safety and serum chemistry, and hematology parameters were measured routinely. Mild eosinophilia was observed in 6 of the 35 monkeys, which did not correlate with a particular adjuvant regimen and was not observed in the group receiving RBD-scNP + 3M-052-AF. No other vaccine or adjuvant related serum chemistry or hematology changes were observed. No weight loss or adverse effects were observed.

The above data provide the rationale for evaluating 3M-052-AF alone as an alternative to the combination of 3M-052-AF and Alum for use in HIV-1 vaccine trials. While these data were generated with a SARS-CoV-2 RBD immunogen, both RBD and HIV-1 Env are highly glycosylated trimers, and effective elicitation of neutralizing antibodies to these viruses may therefore be supported by similar adjuvant regimens. Additionally, the monoclonal antibodies with the most potent neutralization isolated from the memory B cells of SARS-CoV-2 vaccine recipients have substantial somatic hypermutation, further supporting the concept that the underlying immunologic mechanisms that lead to improved quality of the neutralizing antibody response are likely to apply to both SARS-CoV-2 and HIV (20).

3M-052-AF is a lipid-modified synthetic imidazoquinoline that is a TLR7/8 agonist. The lipid tail of 3M-052-AF was designed to minimize systemic distribution, and this tail associates with a phospholipid excipient, 1,2-Distearoyl-

sn-glycero-3-phosphoglycerol (DSPG) to create an aqueous nanosuspension formulation (14). In a mouse study of 3M-052 formulated with phosphatidylcholine (a similar phospholipid) instead of DSPG, subcutaneous administration of 25 mcg of 3M-052 in mice did not induce circulating TNF $\alpha$ , indicating an absence of a systemic proinflammatory effect (15). Additionally, in a study performed by Charles River for 3M, localization of radiolabeled 3M-052 (350 mcg) formulated in sesame oil was measured after subcutaneous administration in Sprague Dawley Rats. In this study, concentrations of total radioactivity at the dose site were more than 100-fold higher than the concentrations of radioactivity observed in the sampled tissues at all times, up to 14 days. Notably, clinical safety of the DSPG component of 3M-052-AF has been demonstrated in the liposomal formulation of amphotericin B (Ambisome) which contains DSPG. Ambisome has reduced incidence of adverse events compared to amphotericin B deoxycholate upon i.v. administration (19, 21). Even though the evaluation of 3M-052-AF biodistribution (without Alum) is not yet available, data with other formulations of 3M-052 without Alum, as mentioned above, indicate that the activity of this adjuvant is predominantly localized.

## 2.3 Rationale for Schedule

To match the schedule used in other comparable trials (HVTN 115) and pre-clinical studies, the CH505 TF chTrimer protein will be administered IM into both deltoids in a volume of 1 mL divided into two 0.5 mL injections administered in the left and right deltoid at a dose of 150 mcg per deltoid (total dose 300 mcg) at months 0, 2, 4, 8, and 12. The rationale for splitting the dose between deltoids is based upon both theoretical and practical considerations. Theoretically, having more lymph nodes engaged in the germinal center process should allow for more clonal selection and competition, leading to additional somatic hypermutation necessary for bnAb maturation. Practically, splitting the dose should decrease the potential for localized reactogenicity in this first in human trial and facilitate sampling of lymph nodes via Fine Needle Aspiration in HVTN 300 Part A (see Section 2.6). Additionally, in pre-clinical studies in rhesus macaques, antibody titers rose with each subsequent injection up to five boosts. This is in contrast to previous experience with other adjuvants.

## 2.4 Rationale for Dose of Protein

The 300 mcg dose of protein has been selected on the basis of promising preclinical data generated from rhesus macaques (see Section 2.1, Figure 2-2 and Figure 2-3) and reassuring safety data generated from analogous studies of recombinant trimers used in clinical trials. These studies include IAVI W001 (300 mcg) and HVTN122 (300 mcg) (see Section 2.2).

**Clinical Data:** We anticipate summaries of preliminary clinical safety data from the HVTN 122 and IAVI W001 studies to support the protein trimer dose selected for this study and the IND application.

For additional information, see the Investigator's Brochure (IB).

## **2.5 Rationale for Dose of Adjuvant**

The 5 mcg dose of 3M-052-AF adjuvant has been selected based on previous preclinical experience (see Section 2.1, [Figure 2-2](#) and [Figure 2-3](#)) and dose selection in HVTN 137 (see [Table 2-2](#)). The 500 mcg dose of alum (ie, aluminum content by weight) adjuvant also matches the regimen in HVTN 137.

The 3 mcg dose of 3M-052-AF was selected for use in HVTN 300 Part B in order to compare 3 mcg and 5 mcg doses to determine if the reactogenicity profile seen with 5 mcg of 3M-052-AF/Alum can be reduced with 3 mcg 3M-052-AF ( $\pm$  Alum) while maintaining similar adjuvant activity. Results from this trial will be compared to data from Part A of the HVTN 300 trial.

## **2.6 Rationale for Fine Needle Aspiration**

To improve assessment of the effects of CH505 TF on B cell lineage development, this protocol will employ fine needle aspiration (FNA) of an axillary lymph node proximal to the site of vaccine administration in study participants enrolled in Part A ([Appendix A](#)). FNA will be performed after the 3rd dose of CH505 TF chTrimer has been administered. The germinal center response, which occurs exclusively in the lymphatic tissue, is critical for directing B cell lineage development. Havenar-Daughton and colleagues have employed repeated direct probing of germinal center responses by fine needle lymph node aspirates in nonhuman primate (NHP) studies and found that induction of neutralizing antibodies against Tier 2 autologous HIV strains best correlated with germinal center B cell magnitude and Env-specific CD4+ Tfh cells (22). Similar sampling strategies are under evaluation in licensed vaccine and early phase human HIV vaccine studies and are planned in this protocol (23).

## **2.7 Rationale for Leukapheresis**

To assess the expansion of rare precursor B cell populations that occur at a frequency of approximately  $\sim 1/20$  million cells, large numbers of peripheral blood mononuclear cells (PBMCs) are required. Leukapheresis can provide 6-10 billion PBMCs without depleting red blood cells or other blood components. There are approximately 1 million PBMCs per milliliter of blood and therefore peripheral blood sampling at volumes associated with typical blood donation ( $\sim 500$  mL) would not provide sufficient PBMC numbers. Furthermore,

leukapheresis is associated with fewer adverse events when compared to blood donation. Hence this protocol will employ leukapheresis in study participants enrolled in Part A ([Appendix A](#)) to ensure adequate specimens for analysis of rare precursors. Leukapheresis will be performed at screening and after the 4th dose of CH505 TF chTrimer has been administered. The rationale for performing leukapheresis three weeks after the 4th dose is based upon detailed preclinical investigations into the kinetics of the germinal center response in rhesus macaques (see Section [2.1](#) and (24)).

## **2.8 Risks and benefits**

### **2.8.1 Potential risks**

In addition to risks associated with 3M-052-AF + Alum adjuvants (see Section [2.2](#)), frequent potential side effects resulting from other intramuscular (vaccines) and subcutaneous (local anesthetic prior to FNA) injections include stinging, discomfort, redness of skin, or mild bruising at injection site.

Frequent potential side effects resulting from other intramuscular (vaccines) and subcutaneous (local anesthetic prior to FNA) injections include stinging, discomfort, redness of skin, or mild bruising at injection site.

Less frequent side effects from other intramuscular vaccines include: fever, chills, rash, aches and pains, nausea, dizziness and fatigue. If these occur, they will be monitored, but with other vaccines, these effects are generally short term, mild to moderate in severity, and usually do not require treatment.

Rare risks with any injection procedure include infection at the site of injection. Signs of infection at the injection site include severe pain, erythema, induration, warmth or drainage. There are rare reports of anaphylaxis with many vaccines. There may be side effects from the study products which may be serious or life threatening that we do not know about yet.

If antibodies elicited by the study vaccine result in a positive or indeterminate HIV test (ie, vaccine-induced seropositivity or VISP), this may have a negative impact on employment, health care, insurance, travel, and personal relationships. HIV PCR will be used to exclude or confirm HIV infection.

Alum adjuvant: For more than 90 years, Alum has been used as an adjuvant in commercial vaccines. Hundreds of millions of people have gotten vaccines containing Alum. Side effects are generally limited to minor local reactions at the injection site.

Blood drawing may cause pain, bruising, fainting, and, rarely, infection at the site where the blood is taken. Leukapheresis can also cause pain, bruising, and, rarely

infection. Additional risks may depend on local leukapheresis procedures. Fainting can also occur, but occurs less frequently than with blood drawing.

Fine needle aspiration of lymph nodes can uncommonly cause pain, bruising, and/or bleeding at the site where the needle is inserted. Similar to any procedure where a needle is inserted into the skin (such as vaccination, as described above), there is a rare risk of localized infection. The local anesthetic rarely can cause arm numbness or weakness.

**Risks during Pregnancy:** Because possible effects of the study vaccine on a fetus or nursing infant are unknown, persons assigned female sex at birth who have reproductive potential will be tested for pregnancy at screening and prior to administration of each dose of study vaccine. Such persons will be asked to notify the site immediately if they suspect or learn they are pregnant during this study. In case of pregnancy, participants will continue to be followed for safety and the participant will not receive any additional vaccinations. The participant will be contacted about the outcome of a pregnancy that begins during the study.

**Other Risks:** The medical tests performed as part of this research protocol may result in new diagnoses or abnormal values without clinical significance (“false positives”). Depending on the medical findings and consequences of being provided with the results of these tests, the study participant may view this as either a risk or a benefit. Any such information will be shared and discussed with the participant and, if requested by the participant, may be forwarded to the primary health care provider for further workup and management.

Participants in this study risk experiencing discrimination or other personal problems that may result from study participation itself: these are known collectively as negative social impacts. The HVTN clinical research site (CRS) is obliged to provide advocacy for and assistance to participants regarding these negative social impacts associated with the vaccine trial. If HVTN CRS staff have questions regarding ways to assist a participant dealing with a negative social impact, a designated HVTN Core representative can be contacted.

## **2.8.2 Benefits**

Study participants will not receive direct health benefit from study participation. Others may benefit from knowledge gained in this study that may aid in the development of an HIV vaccine. The investigational vaccine is not expected to provide protection from HIV infection.

Participants may benefit from more frequent counseling, laboratory tests and physical exams while enrolled in the study. Participants may also experience positive social impacts as a benefit of study participation. When asked, participants say that being in a study made them feel good about helping others, increased their knowledge about HIV, and improved their self-esteem.

## **2.9 Assessment of immunogenicity endpoints**

The primary immunogenicity endpoint assay will measure the frequency of CH505TF- and epitope-specific memory B cells after vaccination). Evaluation of cellular responses will be performed on all samples after vaccination and compared to each participant's baseline. Multiparameter flow cytometry will be used to assess the frequency of CH505TF- and epitope-specific IgG+ B cells. The antigen-specific B cell phenotyping assays will be performed at the Fred Hutch HVTN laboratory.

Lymphocytes from an axillary lymph node obtained by fine needle aspiration (FNA) of the node will be examined for a germinal center phenotype (germinal center B cell) via flow cytometry three weeks after the 3rd vaccination.

Additional assays may be performed on selected responders and at additional timepoints at the discretion of Protocol Team leadership based on its evaluation of primary results following the third vaccination (see [Section 3.1](#)).

### **3 Objectives and endpoints for Part A and Part B**

#### **3.1 Primary objectives and endpoints**

*Primary objective 1:*

To evaluate the ability of the vaccine regimen to elicit CD4 binding-site, V2 apex and V3 glycan (bnAb region at the base of the V3 loop), and CH505TF-specific memory B cells

*Primary endpoint 1:*

Flow cytometry analysis of the frequency of the CD4 binding-site, V2 apex and V3 glycan (bnAb region at the base of the V3 loop), and CH505TF-specific IgG+ B cells

*Primary objective 2*

To evaluate the ability of the vaccine regimen to elicit autologous tier 2 virus neutralizing antibodies

*Primary endpoint 2:*

Response rate and magnitude of serum antibody neutralization of vaccine-matched tier 2 HIV-1 strains as measured by TZM-bl assay

*Primary objective 3:*

To evaluate the safety and tolerability of a 300 mg dose of CH505 TF chTrimer admixed with different adjuvant regimens

*Primary endpoint 3:*

Local and systemic reactogenicity signs and symptoms will be collected for a minimum of seven days following receipt of any study vaccine.

Serious adverse events (SAEs), medically attended adverse events (MAAEs), adverse events of special interest (AESIs) and AEs leading to early participant withdrawal or permanent discontinuation which will be collected throughout the study and for twelve months following any receipt of study product. Additionally, all adverse events will be collected for 30 days after any receipt of study vaccination.

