Remote or in-person contact between the participant and the site staff should take place at least once on the third- or fourth-day following vaccination. The reactogenicity assessment period is seven days following vaccine administration. Clinicians will follow and collect resolution information for any reactogenicity signs and symptoms that have not resolved within 7 days.

Any postvaccination reaction grade 2 or higher will be assessed by a clinician within 48 hours after onset, unless the reaction is improving and/or has completely resolved. Additionally, other clinical concerns may prompt a study visit based on the judgment of a study clinician.

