## 9 Safety and adverse events

### 9.1 Adverse events

Unsolicited AEs will be collected over a period of 30 days after each vaccination. All collected AEs are captured in the clinical database on the appropriate CRF. Clinic staff should evaluate every AE to determine if (1) the AE meets the requirements for expedited reporting (see Section 9.2.1), (2) if the AE meets the criteria for a safety pause/prompt AE review (see Section 9.7), (3) if the AE meets the criteria for an MAAE, and (4) if the AE is a potential immune-mediated disease that may be listed as an AE of special interest (AESI). A sample list of AESIs is provided in [Appendix H](#).

In addition, a limited set of AEs will be collected and reported for 12 months following the any vaccine administration

- SAEs/EAEs,
- AESIs,
- MAAEs (defined as any adverse events leading to an unscheduled visit to a healthcare professional)
- AEs leading to early participant withdrawal or early discontinuation of study vaccine(s) administration.

Adverse events (AEs) will be graded according to the Division of AIDS (DAIDS) Table for Grading the Severity of Adult and Pediatric Adverse Events, Corrected Version 2.1 (<https://rsc.niaid.nih.gov/clinical-research-sites/daids-adverse-event-grading-tables>), with the following exceptions:

- Unintentional Weight Loss is required to be reported as an AE only if it is considered to be potentially deleterious to the participant's health (see HVTN 300 SSP);
- Creatinine is required to be reported as an AE only if it is gradable per the increase from local lab ULN parameter. Do not grade elevated creatinine based on the change from the baseline parameter.
- Do not grade creatinine clearance or eGFR based on the change from the baseline parameter. Do not grade on the basis of eGFR if there is clinical concern for kidney injury.

- Injection Site Erythema or Redness and Injection Site Induration or Swelling will not consider surface area and interference with usual social and functional activities such that:
  - Grade 1 is: 2.5 to < 5 cm in diameter;
  - Grade 2 is:  $\geq 5$  to < 10 cm in diameter;
  - Grade 3 is:  $\geq 10$  cm in diameter OR Ulceration OR Secondary infection OR Phlebitis OR Sterile abscess OR Drainage;
  - Grade 4 is: Potentially life-threatening consequences (eg, abscess, exfoliative dermatitis, necrosis involving dermis or deeper tissue);

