## Appendix A Schedule of procedures for Part A

Visit Number	01	02	03	04	05	06	07	08	09	10	11	12	AESI 
Study Week		0	2	8	10	16	18	32	34	52	54	80	104
Study Month		0	0.5	2	2.5	4	4.5	8	8.5	12	12.5	18	24
Study Day	-56 to 0	0	14	56	70	112	126	224	238	364	378	560	728
Procedure	Screen 	Vac 1		Vac 2		Vac 3		Vac 4		Vac 5			
Study procedures													
Assessment of Understanding	√												
Informed consent	√												
Medical history 	√												
Physical exam 	√	√	√	√	√	√	√	√	√	√	√	√	
Contraception status assessment 	√	√		√		√		√		√			
Risk reduction counseling 	√	√	√	√	√	√	√	√	√	√	√	√	
Concomitant medications 	√	√	√	√	√	√	√	√	√	√	√	√	
Adverse Events (AEs)		√	√	√	√	√	√	√	√	√	√		
AESIs/MAAEs/SAEs		√	√	√	√	√	√	√	√	√	√	√	√
Vaccination 		√		√		√		√		√			
Reactogenicity assessment 		√		√		√		√		√			
Clinical labs	Tube												
Pregnancy test (urine or serum) 	√	√		√		√	√	√	√	√		√	
HBsAg/anti-HCV 	SST	5											
HIV screening test 	SST	5											
CBC/Differential 	EDTA	5	5		5		5		5		5		
ALT & Creatinine 	SST	5	5		5		5		5		5		
HIV diagnostic test	EDTA					10		10		10		20	
Research samples													
PBMC for assays & storage	ACD		136		136		136				178.5	178.5	
Serum for assays and storage	SST		34	34	34		34		34		34	34	
Leukapheresis			√ 						√				
Fine Needle Aspiration 							√						
Daily volume (mL)	20	34	180	0	180	10	180	10	44	10	222.5	232.5	
56-day total volume (mL)	20	54	234	234	360	190	370	10	54	10	232.5	232.5	

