## Appendix C Visit windows for Part A and Part B

Visit Number	Visit Type	Lower Allowable Window (-)	Lower Target Window (-)	Target Day*	Upper Target Window (+)	Upper Allowable Window (+)
01.0	Screening	-56	-	0	-	+0
02.0	Enrollment/Vaccination 1	-	-	0	-	-
03.0	2 weeks post-vaccination 1		-4	14	+4	+7
04.0	Vaccination 2		-7	56	+9	+14
05.0	2 weeks post-vaccination 2		-4	70	+4	+7
06.0	Vaccination 3	-21	-14	112	+14	+21
07.0**	2 weeks post-vaccination 3 Primary Immunogenicity	-	-4	126	+4	+21
08.0	Vaccination 4	-28	-14	224	+14	+28
09.0	2 weeks post-vaccination 4	-	-4	238	+4	+7
10.0	Vaccination 5		-28	364	+28	
11.0	2 weeks post-vaccination 5		-4	378	+4	+7
12.0	Final Visit	-28	-14	560	+14	+28
AESI	AESI Contact	-28	-14	728	+14	+28

\* All target dates are relative to Day 0, with the exception of the post-vaccination visits, visits 3.0, 5.0, 7.0, 9.0, and 11.0 which are relative to the vaccination immediately preceding the visit.

\*\* Target date for FNA is three weeks post 3rd vaccination, see HVTN 300 Study Specific Procedures (SSP) for more details.

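### About half of the 30-day adverse event window after dose 5 has no scheduled all-AE assessment, although the primary safety endpoint covers 30 days after every dose

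*Protocol*

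**What the plan says.** The 30-day commitment appears three times. Primary endpoint 3 in Protocol 3.1 reads "Additionally, all adverse events will be collected for 30 days after any receipt of study vaccination". Protocol 9.1 reads "Unsolicited AEs will be collected over a period of 30 days after each vaccination". SAP Section 4 repeats the endpoint. None of these exempts the last dose.

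A narrower group of events is followed for longer. Under Protocol 9.1, "a limited set of AEs will be collected and reported for 12 months following the any vaccine administration": SAEs/EAEs, AESIs, MAAEs, and AEs leading to withdrawal or to stopping vaccination.

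Appendices A and B (schedules for Parts A and B) use separate rows for the two groups of events:

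- The general AE row is ticked at Visits 02 to 11. It is blank at Visit 12 (Day 560) and at the AESI contact (Day 728).
- The row labelled "AESIs/MAAEs/SAEs" is ticked at Visits 02 to 12 and at the AESI contact.

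Appendix C describes Visit 11 as "2 weeks post-vaccination 5". Its target is Day 378, with a target window of -4/+4 days and an upper allowable limit of +7. Its timing is "relative to the vaccination immediately preceding the visit". Dose 5 is at Day 364.

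**The concern.** After dose 5 the schedule gives less follow-up than the endpoint promises. The general AE row stops half-way through the 30-day window, and no later visit asks about the rest of it. The two AE rows are kept distinct and show the same pattern in both Parts, so the blank cells do not look like a table-reading fault.

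This is a primary safety endpoint in a first-in-human trial, and the gap follows the last of five doses. A reader of the final safety tables would take them to reflect 30 days of comparable follow-up after every dose, and nothing in the SAP says otherwise. Weekly review by the Protocol Safety Review Team is also set to run through two weeks after the last participant's final injection (Protocol 9.3.1). For that participant it ends at about the same point.

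**Working it through.** **Inputs.** Dose days 0, 56, 112, 224 and 364, and Visit 11 at Day 378 (Appendices A to C). Visit 11 limits are -4, +4 and +7 days (Appendix C). No lower allowable limit is printed for Visit 11, so -4 is taken as the earliest. The window length is 30 days (Protocol 3.1 and 9.1).

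**1. The plan's own figure.** Visit 11 minus dose 5 = 378 - 364 = 14 days, which agrees with the two weeks stated in Appendix C.

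**2. Which doses are affected.** For each dose, find the first visit with the general AE row ticked on or after dose day + 30.

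| Dose | Day | Window ends | First such visit | Days after window ends |
|---|---|---|---|---|
| 1 | 0 | 30 | Visit 04 (Day 56) | 26 |
| 2 | 56 | 86 | Visit 06 (Day 112) | 26 |
| 3 | 112 | 142 | Visit 08 (Day 224) | 82 |
| 4 | 224 | 254 | Visit 10 (Day 364) | 110 |
| 5 | 364 | 394 | none | none |

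**3. Size of the gap.** Uncovered days = 30 - days from dose 5 to Visit 11.

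| Visit 11 timing | Days after dose 5 | Uncovered days | Share of 30 |
|---|---|---|---|
| -4 | 10 | 20 | 67% |
| Target | 14 | 16 | 53% |
| +4 | 18 | 12 | 40% |
| +7 | 21 | 9 | 30% |

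**4. Share of all promised follow-up.** The doses are at least 56 days apart at target, so the windows do not overlap and five doses give 5 x 30 = 150 days. The gap is 16/150 = 10.7% at target, with a range of 9/150 = 6.0% to 20/150 = 13.3%.

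**5. What the gap contains.** "The reactogenicity assessment period is seven days following vaccine administration" (Protocol 8.3), so diary reactogenicity falls wholly before Visit 11. The four classes followed for 12 months are also unaffected. What remains exposed at target dates is AEs with onset about 15 to 30 days after dose 5 that are non-serious, not of special interest, not medically attended, and do not lead to withdrawal or discontinuation.

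**6. Recall if Visit 12 were used.** At target dates Visit 12 is 560 - 364 = 196 days after dose 5, which is 196 - 30 = 166 days after the window closes, and longer for earlier onsets. The shortest gap within the windows pairs dose 5 at Day 392 (364 + 28) with Visit 12 at Day 532 (560 - 28): 532 - (392 + 30) = 110 days.

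**The case against.** **The ticks are not the collection rule.** A schedule shows what is done at visits; the duty to collect comes from Section 9.1 and is not limited to ticked visits. This stands. A reader might infer that AEs from the second half of the dose 5 window are never collected. The documents do not support that, because an event reported on day 20 after dose 5 is in scope. What is missing is a scheduled contact at which participants are asked.

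**Visit 12 could still bring events to light.** It includes concomitant medications and a complete physical examination, and an interim history may be taken (Appendices A and B, with footnotes). This is true, but it is incidental, months later, and no substitute for an AE question.

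**No planned table compares doses.** A reader might also infer that AE rates after dose 5 will look falsely lower than after doses 1 to 4. Protocol 6.2.3 and SAP 10.2 count each participant once per AE, under maximum severity or strongest causal relationship, and SAP 11.1 lists no AE table by dose. A dose 5 distortion arises only if AEs are later split by dose. The schedule gap is also the same in all four groups, so it does not by itself bias comparisons between them.

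**Doses 3 and 4 also rely on recall.** Their windows are closed only 82 and 110 days later at target. This weakens any sharp contrast, but those visits do carry a scheduled AE assessment and dose 5 has none.

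**Not everyone is exposed.** Only dose 5 recipients are affected. Participants can stop or miss vaccinations (Protocol 5.2.2 and 5.2.3), so 48 is a ceiling at target enrolment.

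**The Study Specific Procedures are not available here.** They may contain a Day 30 contact, and this cannot be checked. If they do, the protocol schedules should still show it.

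**Conclusion.** The text and the schedules conflict, and the conflict survives these objections. Both schedules lack an all-AE assessment after Visit 11. At target dates 16 of the 30 days after dose 5 (53%; 9 to 20 days across the Visit 11 windows) therefore have no scheduled elicitation of AEs outside the classes followed for 12 months.

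The likely effect is a modest under-count of such AEs in the per-participant tables. Its size cannot be derived from the documents, because it depends on how many participants report unprompted. As an assumption, suppose onset is uniform over the 150 promised days in a participant who receives all five doses. The share of these events missed then lies between 0, if all are reported unprompted, and 10.7% at target dates (13.3% with Visit 11 at its earliest), if none surface otherwise.

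The point should be fixed, but it does not undermine the capture of serious, special-interest or medically attended events or of reactogenicity. It rests on the schedules as printed and on there being no additional contact in the Study Specific Procedures.

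**What to change.** Reconcile Protocol 3.1 and 9.1, Appendices A and B, and SAP Section 4.

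- **Preferred:** add a remote all-AE contact at or just after Day 30 post-dose 5 (Day 394 at target). Protocol 8.2 already permits remote visits. The uncovered share falls to 0 of 30 days.
- **Second best:** tick the general AE row at Visit 12 in both schedules, with a specific question on onset within 30 days of dose 5. This closes the gap on paper but relies on recall of about 166 days or more at target dates.
- **For participants already past that point:** state in the SAP and in the safety report that scheduled all-AE elicitation after dose 5 ended at Visit 11. If AEs are ever shown by dose, repeat the statement beside that display.

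The cost is one short call or one added question per participant, a minor protocol modification, and a sentence in the SAP and in the safety report.
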